This clinical trial will help clarify the role of multi-ingredient supplements containing amino acids, vitamins, and minerals in the prevention and management of CVD and CVD risk factors.

RESEARCH OBJECTIVES

The overall objective of this study is to determine whether daily supplementation with the dietary supplement Cardioflex for 90 days will reduce risk factor biomarkers for CVD in adults aged 30–65 years old.

The primary objective is to determine whether daily supplementation with the dietary supplement Cardioflex will improve their plasma lipid profile (total cholesterol, HDL-cholesterol, LDL-cholesterol, triglycerides, lipoprotein A).

The secondary objectives are to determine if Cardioflex supplementation will improve anthropometric measures (waist circumference, body mass index), cardiac measures (heart rate, heart rate variability, accelerated plethysmography (APG age, which measures the biological age of arteries), blood pressure), and inflammatory and endothelial function biomarkers (C-reactive protein, IL-6, sICAM-1, sVCAM-1,) and assess the safety of the supplement by measuring serum levels of liver and kidney enzymes (alanine transaminase; ALT, aspartate transaminase; AST, lactate dehydrogenase; LHD, blood urea nitrogen; BUN, and creatinine). To quantify confounding variables, participants were asked to record everything they ate and drank in a food log and wore a pedometer to

track total steps on day 1 (beginning), day 45 (mid-point) and day 90 (end) of the study.

HYPOTHESES

- Participants who consume one serving (10 g) of Cardioflex per day, the label recommended dosage, will have improved lipid profile, as reflected by lower levels of total cholesterol, LDL-cholesterol, triglycerides, and lipoprotein A, and higher HDL-cholesterol than participants who consumed the placebo.
- Participants who consume one serving of Cardioflex per day will have improved cardiac health, as measured by lower blood pressure, higher HRV, lower APG age, and lower levels of inflammation biomarkers (C-reactive protein, IL-6, sICAM-1, and sVCAM-1) than participants who consumed the placebo.
- No significant changes will be seen in anthropometric measures (waist circumference, body mass index) or liver and kidney functions biomarkers (ALT, AST, LHD, BUN or creatinine) between the Cardioflex and the placebo group.

STUDY DESIGN

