To determine the effects of Cardioflex on CVD risk, the dependent variables tested included anthropometrics (weight, height, waist circumference), cardiovascular parameters (blood pressure, heart rate, HRV, APG age), dietary intake, plasma lipid profile (total cholesterol, HDL-cholesterol, LDL-cholesterol, triglycerides, lipoprotein A), and inflammatory and endothelial function biomarkers (C-reactive protein, IL-6, sICAM-1, sVCAM-1). Anthropometrics were included because large scale epidemiological studies have shown correlations between CVD mortality and BMI (Valavanis, Mougiakakou, Grimaldi, & Nikita, 2010) and increased waist circumference is recognized as a major cardiometabolic risk factor (Tchernof & Despres, 2013). Cardiovascular parameters carry valuable information for the prediction of long-term and near-term CVD risk. Blood

pressure is a consistent risk factor for the development of atherosclerosis (Lu, Cassis, & Daugherty, 2007). A higher resting heart rate is linked with greater CVD risk (Fox et al., 2007). Reduced HRV is associated with an increased risk for coronary heart disease and CVD mortality (Liao et al., 1997). Arterial elasticity is an established risk factor to predict future CVD events (Glasser et al., 1997). Lipid profile is recognized as an established risk factor in the development and progression of CVD (Graham, Cooney, Bradley, Dudina, & Reiner, 2012; Jellinger et al., 2012). Inflammation and endothelial function play a significant role in developing atherosclerosis, and risk of future cardiovascular events (Jarvisalo, Juonala, & Raitakari, 2006).

PARTICIPANTS

Recruitment of study participants employed several strategies including email, flyers, and in-person presentations. The study eligibility criteria were adult men and women between the age of 30-65 years old, perform less than 150 minutes of moderate or vigorous physical activity per week, have not used prescription cholesterol or blood pressure medication in the last 3 months, be willing to stop taking any dietary supplements during the study period of 90 days, not pregnant nor planning on getting pregnant during the study, and an APG type of D, E, F or G and/or an HDL-cholesterol to total cholesterol ratio of ≤ 24 percent.

Participants were stratified (male/female) and randomized (block size = 5) to the study treatments using a computer-generated randomization (www.randomizer.org) numbering system.

SAMPLE SIZE

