A sample size calculation was completed using a standard sample size in equation 1 to determine the number of participants needed for the study. With $\alpha = .05$ and $\beta = .90$ and a 12% mean decrease of cholesterol using previously published data (Hobbs et al., 2014) in the supplementation group, we calculated that we would need 60 subjects to reach statistical significance. With an expected attrition rate of 20%, we determined that 72 participants needed to be recruited.

$$n = \frac{2(Z_{\alpha} + Z_{1-\beta})^2 \sigma^2}{\Delta^2}$$

Equation 1 - Estimated sample size equation

Z_{α} = constant to the accepted error, $Z_{1-\beta}$ = constant according to power, σ = standard deviation, Δ = effect size

Overall, 90 adults were screened for eligibility, with 75 adults being deemed eligible. At the time of starting the study 69 adults chose to participate, and 6 eligible adults chose not to participate for personal reasons not related to the study.

STUDY PROCEDURES AND ASSESSMENTS

BLOOD COLLECTION

Blood was drawn at 3 time points in the study – the assessment for eligibility for entry into the study, baseline, and end of the 90-day supplement period. All blood samples were collected in the morning after at least 8 hours overnight fast. The participants reported to the RCFFN at the University of Manitoba Ft. Garry Campus. Blood samples were taken by venipuncture from an antecubital vein into serum tubes by a certified phlebotomist. For eligibility assessment, one 5mL serum tube was withdrawn. For clinical trial baseline and endpoint measurements, two 10mL serum tubes, and one 5mL serum tube, totaling 25mL of blood was withdrawn from each participant. Samples were centrifuged at 4100g for 10 minutes. The plasma was allocated into Eppendorf tubes and frozen at -86 ° C for later analysis.

Cardiac Measurements

Participants were required to sit for a minimum of 5 minutes rest at the beginning of each assessment session. Blood pressure was measured at the brachial artery of the left arm, using an automatic sphygmomanometer (Series 10, Omron). The blood pressure of each participant was taken three times, and the average was recorded. Accelerated plethysmograph (APG) type, HR, and HRV were assessed using a Meridian digital pulse-wave analyzer (DPA) machine (Long Life Cardio LLC, USA). HRV was measured using the standard deviation of all of the RR intervals (the distance between each heartbeat) after 5 minutes of recording.

ANTHROPOMETRICS

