Serum concentrations of total cholesterol, triglycerides, HDL-cholesterol, BUN, creatinine, AST, ALT, and LDH were measured using automated enzymatic methods on a Vitros-350 chemistry analyzer. LDL-cholesterol levels were estimated using the Friedewald formula: $\text{LDL-cholesterol} = \text{Total cholesterol} - \text{HDL-cholesterol} - \text{triglycerides}/2.2$ (Rifai N, 2006).

CRP, IL-6, SiCAM, and SvCAM were measured using Meso Scale Discovery V-PLEX assays (MSD, Rockville, Md., USA). 25 μL of sample, calibrator, or control was added to each well of a 96-well plate. The calibrator and control were provided by Meso Scale Discovery. The plate was sealed and incubated at room temperature for 2 hours on a plate shaker set to 400 rpm. Next, 25 μL of detection antibody was added to each well. The plate was sealed and incubated for 1 hour at room temperature on a plate shaker set to 400 rpm. Finally,

150 μL of read buffer was added to each plate and the plates were read on the Meso Scale Discovery QuikPlex SQ 120 instrument. All blood analysis was done in duplicates, with the average of the two values being recorded.

Lipoprotein A was measured using ELISA assay (Human lipoprotein A No.ab212165, Abcam Trading Company, Ltd, China). 50 μL of sample or standard and 50 μL of antibody were added to each well of a 96-well plate. The plate was incubated at room temperature for 1 hour on a plate shaker set to 400 rpm. Next, 100 μL of TMB substrate was added to each well, followed by incubating the plate for 10 minutes on a plate shaker set to 400 rpm. Finally, 100 μL of stop solution was added to each well and the plate was read with a microplate reader set to 450 nm (autoreader EL311; Bio-tek instruments). All blood analysis was done in duplicates, with the average of the two values being recorded.

Coenzyme Q10 was measured using ELISA assay (Human CoQ10 No. CSB- E14081h, Cusabio® Biotech Co., Ltd, China). 50 μL of sample or standard and 50 of HRP-conjugate was added to each well of a 96 well plate. The plate incubated for 40 minutes at 37°C. Next, 90 μL of TMB substrate was added to each well. The plate incubated for 20 minutes at 37°C. Finally, 50 μL of stop solution was added to each well, and the plate was read with a microplate reader set to 450 nm (autoreader EL311; Bio-tek instruments). The blood analysis was done in duplicates, with the average of the two values being recorded.

STATISTICAL ANALYSIS

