Data were analyzed using IBM SPSS Statistics (v.25). Significance was determined using the treatment effect between groups. The significance value was set at $p \leq 0.05$. An independent t-test showed that there were no statistical differences between the starting points of the two groups ($P > 0.05$), indicating that the two groups were indistinguishable from each other.

The primary analysis was conducted using the post-treatment biomarker value, comparing the two groups, and controlling for their baseline values by using analysis of covariance. Analysis of covariance examines the differences in the mean values of the dependent variable that is related to the effect of the controlled independent variable while taking into account the influence of the uncontrolled variables. In this study, the dependent variable was the biomarkers being tested, the controlled independent variable was the treatment given and the uncontrolled variables were the baseline differences between participants. Analysis of covariance makes the assumption that the data is normally distributed in equal variances. To check the assumption of normal distribution, a Shapiro–Wilk test was performed. To check the assumption of equal variance, a Levene's test was performed.

Results are given as mean \pm standard deviation (SD). Outliers were determined as values greater or less than the mean \pm 3*SD (Jones, 2019). If outliers were present, they were removed, and the results were recalculated. For each parameter, the percent change was calculated by equation 3.

$$\% \text{ Change} = \frac{\text{Final Value} - \text{Starting Value}}{\text{Starting Value}} \times 100$$

Equation 3: Percent change calculation

REFERENCES

- Benjamin, E. J., Muntner, P., Alonso, A., Bittencourt, M. S., Callaway, C. W., Carson, A. P., . . . Stroke Statistics, S. (2019). Heart Disease and Stroke Statistics-2019 Update: A Report From the American Heart Association. *Circulation, 139*(10), e56-e528. doi:10.1161/CIR.0000000000000659
- Black, A. E. (2000). Critical evaluation of energy intake using the Goldberg cut-off for energy intake:basal metabolic rate. A practical guide to its calculation, use and limitations. *Int J Obes Relat Metab Disord, 24*(9), 1119-1130. doi:10.1038/sj.ijo.0801376
- Canada, S. (2020). Table 13-10-0801-01 Leading causes of death, total population. Retrieved from <https://www150.statcan.gc.ca/t1/tb11/en/tv.action?pid=1310080101>

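### The 3-SD deletion rule has no exemption for the liver and kidney safety markers, so individual abnormal values are removed or hidden in an arm mean

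*Combined protocol and SAP*

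**What the plan says.** Research Objectives states that the study will "assess the safety of the supplement by measuring serum levels of liver and kidney enzymes", naming ALT, AST, LDH, BUN and creatinine. Hypotheses then predicts no significant change in "liver and kidney functions biomarkers (ALT, AST, LHD, BUN or creatinine) between the Cardioflex and the placebo group". The available text describes no other safety measure.

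Blood Analysis confirms that "BUN, creatinine, AST, ALT, and LDH were measured using automated enzymatic methods". Blood Collection gives three draws: eligibility, "baseline, and end of the 90-day supplement period". Each person therefore has one on-treatment value.

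Statistical Analysis describes a single method: ANCOVA of the post-treatment value on arm, adjusted for baseline, at p ≤ 0.05. It is reported as mean ± SD with a percent change for each parameter. It says that "the dependent variable was the biomarkers being tested" and that "Significance was determined using the treatment effect between groups". Values more than 3 SD from the mean count as outliers: "If outliers were present, they were removed, and the results were recalculated". The section does not say whether the SD is taken within arm or over both arms, whether the rule is applied to baseline or final values, or whether it is applied once or repeatedly. It gives no exemption for the safety markers, and no reference limit, count, shift table or listing.

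**The concern.** A comparison of means suits lipids, where the question is whether the whole group shifts. Organ injury may instead show as a large rise in a few people. Those are the values that a 3-SD rule picks out and removes. A moderate rise that survives the rule is averaged over the arm.

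The predicted safety result is a non-significant difference. The stated procedure would usually return that result whether or not one or two people on Cardioflex had a marked rise. At stake is the safety statement: a participant with ALT at several times the limit could be dropped as an outlier while the supplement is reported as showing no significant change. Percent change does not reveal this either, because it does not show whether a value lies outside the reference range.

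**Working it through.** **Plan's own figure.** The plan gives none for the safety comparison. Sample Size gives 60 in total for cholesterol, without an SD. I use it only for the arm size: 60 / 2 = 30 per arm, which assumes equal allocation.

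**Assumed inputs (none are in the documents).** Log-normal values; two-sided p ≤ 0.05, counted only when Cardioflex is higher; one deletion pass on baseline and day-90 values. ALT base case: mean 25, SD 9, limit 45 U/L, baseline to day-90 correlation 0.7. Ranges: ALT SD 9-12; AST 23, SD 6-8, limit 40; LDH 170, SD 30, limit 230; creatinine 75, SD 15 µmol/L; BUN 5, SD 1.3 mmol/L; correlation 0.5-0.85.

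**Step 1. Can the rule reach affected people?** Let k of N values share one very large rise. Their standardised distance from the mean tends to z = √[(N − k)(N − 1) / (kN)].

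- Within an arm, N = 30: k = 1 gives √(29 × 29 / 30) = 5.29; k = 2 gives √(28 × 29 / 60) = 3.68; k = 3 gives √(27 × 29 / 90) = 2.95.
- Both arms, N = 60: k = 5 gives √(55 × 59 / 300) = 3.29; k = 6 gives √(54 × 59 / 360) = 2.97.

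So one or two large values can exceed 3 SD on either reading of the rule.

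**Step 2. How often are the affected values deleted?** For one or two affected people:

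| Marker and rise | Pooled SD | SD within arm |
|---|---|---|
| ALT, 2x limit or more, SD 9 | about 100% | about 95-100% |
| ALT, 2x limit or more, SD 9-12 | 99-100% | 61-100% |
| Creatinine, 2x own baseline | 65-81% | 43-73% |
| Creatinine, 1.5x own baseline | 24-30% | 16-24% |
| BUN, 2x own baseline | 46-57% | 32-50% |
| BUN, 1.5x own baseline | 15-18% | 10-14% |

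The 61% is for two people at exactly twice the limit with SD 12. Deletion is the main problem for large enzyme rises; averaging is the main problem for moderate kidney-marker rises.

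**Step 3. What does the ANCOVA then show?** ALT base case, percentage of trials significant towards harm, for rises to 2x / 3x / 5x the limit (10,000 runs per cell):

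| Affected | Pooled deletion | Within-arm deletion | All values kept |
|---|---|---|---|
| One | 2.6 / 2.4 / 2.5 | 3.3 / 3.1 / 3.2 | 2.8 / 0.7 / 0.0 |
| Two | 2.6 / 2.6 / 2.5 | 4.0 / 3.1 / 3.1 | 7.4 / 3.1 / 0.6 |

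Over all five markers and the input ranges, deletion gives about 2-11% for one or two people. The top, 10.8%, is two people with ALT at 1.5x the limit under within-arm deletion. With no harm the rate is 2.1-3.5%. A separate simulation on a different assumed grid gave 1.1-11.9% with deletion.

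**Step 4. Why keeping the values does not rescue the test.** With values kept and very large equal rises in k of 30, t tends to √[k(n − 1) / (n − k)]. For k = 1 this is √(29/29) = 1.00, and for k = 2 it is √(58/28) = 1.44, against a critical value of 2.00 on 57 df. The SD grows with the mean difference.

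**Step 5. Would a test of counts help?** Against 0 of 30, Fisher's exact p is 1.00, 0.49 and 0.24 for one, two and three cases. It would not.

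**The case against.** **Low power is not specific to this plan.** No between-arm test can flag one or two of 30, and the fix does not change that. This stands. A reader might infer that a better test would detect such cases; Step 5 shows otherwise. What remains is that the plan removes or averages away the individual values and states no other place where they would appear.

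**Detection does not fall to zero under the stated rule.** This also stands. Figures near 0% arise only if extreme values are kept, which is not what Statistical Analysis describes. With deletion the low end is about the no-harm rate.

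**The rule does not remove every abnormal value.** Agreed; see the 1.5x rows in Step 2. Nor do the Step 1 figures cap how many people can be removed: they assume equal rises and a single pass, and the plan does not state the number of passes.

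**The markers are missing from the outcome list in Study Design.** That list begins "the dependent variables tested included anthropometrics (weight, height, waist circumference" and concerns effects on CVD risk, so leaving out safety markers there is not an inconsistency. That the ANCOVA covers them is an inference from the between-group hypothesis and the absence of any other stated analysis.

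**Recalculation may mean that both sets of results exist.** Possibly, but the plan does not say that the results before deletion are reported, and they too would be arm means.

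**The simulation is one path.** The plan also runs Shapiro-Wilk and Levene checks without saying what follows if they fail. The percentages are therefore illustrative.

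**Conclusion.** The concern holds in this form: the only safety measures described are subject to a rule that deletes extreme values, and the only stated summary is an arm mean, with non-significance as the predicted result. Large ALT rises in one or two people are deleted in about 95-100% of cases in the base case. With deletion, a significant result towards harm occurs in about 2-11% of trials per marker, against about 2-3.5% with no harm.

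The percentages rest on assumed marker distributions, limits, correlations and rises, on 30 per arm and on one deletion pass. The absence of an exemption and of any individual-level summary rests on the text alone. A reader might infer that harm occurred and was hidden; the documents report no safety results and do not support that. The primary lipid comparison is not affected by this point. The change is worth making because it is cheap and the safety statement depends on it.

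**What to change.** In Statistical Analysis, exempt ALT, AST, LDH, BUN and creatinine from the 3-SD deletion, and add by arm, descriptively:

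- **Counts.** Number and percentage above the laboratory's upper reference limit and above standard multiples, with exact 95% confidence intervals. For example: 2x and 3x the limit for ALT and AST; 1.5x the limit for LDH and BUN; 1.5x and 2x own baseline for creatinine.
- **Shift table.** Baseline to day 90.
- **Listing.** Every participant who crosses a threshold.

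Base the safety statement on these together with the mean comparison. Use standard published or laboratory multiples, or have an independent party set them, because the text already reports results by arm (the dietary exclusions in Dietary Intake Records and Analysis). The higher multiples are needed because background values cross the plain limit: with no harm, the assumed chance that at least one of 30 exceeds it for ALT is 62%, against 0.2% at twice the limit (9.7% if the mean is 28 and the SD 14).

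**Cost.** A few lines of text, one table and one listing from values already measured; no new samples or assays.

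**Downside.** Counts will be small and intervals wide: 0 of 30 allows up to 1 − 0.025^(1/30) = 11.6%, and 2 of 30 gives 0.8-22.1%. The safety statement becomes more cautious and cannot attribute one to three cases to Cardioflex. With one on-treatment sample, a raised value cannot be confirmed by a repeat.

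### The mean ± 3 SD deletion rule does not exempt the liver and kidney safety markers, so a genuine isolated rise can drop out of the safety summaries

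*Combined protocol and SAP*

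**What the plan says.** The Statistical Analysis section defines outliers by distance alone: "Outliers were determined as values greater or less than the mean" plus or minus three SDs. It then states: "If outliers were present, they were removed, and the results were recalculated".

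The same section describes the ANCOVA, in which "the dependent variable was the biomarkers being tested". It gives the reporting format ("Results are given as mean" with the SD) and adds: "For each parameter, the percent change was calculated by equation 3".

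Research Objectives includes the aim to "assess the safety of the supplement by measuring serum levels of liver and kidney enzymes". The third item under Hypotheses predicts no significant change in anthropometric measures "or liver and kidney functions biomarkers (ALT, AST, LHD, BUN or creatinine) between the Cardioflex and the placebo group" (LHD there is the lactate dehydrogenase that Blood Analysis calls LDH).

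The section does not state:
- whether the 3-SD limits are pooled or per arm;
- whether they apply to baseline values, final values or both;
- whether the check is repeated after a removal;
- how many values were removed;
- whether results with the removed values kept are reported.

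**The concern.** A deletion rule based only on distance from the mean cannot tell a bad measurement from a real response. For a safety marker, one large rise in one participant is exactly what such a rule removes. The liver and kidney markers are the only safety measure named in the available text. It describes no listing of individual laboratory values and no adverse-event analysis, so a deleted value has no other stated place to appear. The stated expectation for these markers is no change, so deleting a treated participant's rise moves the summaries toward the expected answer.

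At stake are the safety estimate and the individual values behind it. The significance test and the efficacy results are much less affected.

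**Working it through.** The plan gives no figure on this point to reproduce, and no mean, SD or distribution for any safety marker. The size must therefore rest on assumptions. Sample Size gives 60 participants needed and 69 who started. The split by arm is not given, so 30 and 34 per arm are used.

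**1. Can the rule remove a single high value at this size?** Let the other n − 1 values have mean 0 and SD 1, and let x be the high value, included in the mean and SD. It is removed when x² > [9(n − 2)/(n − 1)] / [((n − 1)/n)² − 9/n]. For n = 30: 8.690/0.6344 = 13.70, so x > 3.70. For n = 34, 60 and 69 the thresholds are 3.59, 3.29 and 3.25 SDs above the mean of the others. So it can, with per-arm or pooled limits.

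**2. How likely is removal?** Assume lognormal values with log-SD 0.4. In units of the median, the mean is exp(0.08) = 1.083 and the SD is 1.083 × √(exp(0.16) − 1) = 0.451. The cut-off is about 1.083 + 3.70 × 0.451 = 2.75 (per arm, n = 30) or 1.083 + 3.29 × 0.451 = 2.57 (pooled, n = 60). A participant whose own value is multiplied by k is removed with probability about P(Z > ln(cut-off/k)/0.4):

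| Rise | Approximation, per arm / pooled | Simulation, both limits, 30–34 per arm | Simulation, log-SD 0.3–0.5 |
|---|---|---|---|
| 2-fold | 0.21 / 0.27 | 0.24–0.29 | about 0.18–0.45 |
| 3-fold | 0.59 / 0.65 | 0.60–0.66 | about 0.44–0.88 |
| 5-fold | 0.93 / 0.95 | 0.93–0.95 | about 0.80–1.00 |

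The simulation also assumes a baseline–final correlation of 0.7 on the log scale and one pass of the rule. It differs from the approximation because the sample mean and SD vary.

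**3. What does the summary lose?** One 5-fold rise among 30 adds (5 − 1)/30 = 13.3% of the placebo mean to the difference; the simulation gives about 13%. After deletion the estimate is about 0–1%, and the treated SD falls from 85% to 39–40% of the placebo mean. The ANCOVA rejects in 2.0% of runs with all values kept and 4.9–5.7% after deletion. For one 3-fold rise the figures are 4.1% and 5.0–6.0%. The test would usually miss such a case either way.

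**4. What if several values rise together?** Three 5-fold rises add 3 × 4/30 = 40%. After deletion the estimate is 10–21%, and rejection falls from 13% to 5–8%. At least one of the three is removed in 96–100% of runs, but with pooled limits all three go in only 17%. With five 5-fold rises and pooled limits, 2.1 are removed on average and all five essentially never. Partial removal is the usual result.

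**5. Efficacy, at the plan's 12% effect and 30 per arm.** The last column is the range over pooled and per-arm limits.

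| log-SD | Shrinkage of estimate | Rejection, all kept | Rejection after deletion |
|---|---|---|---|
| 0.2 | 0.5–2.7% | 91.6% | 90.8–91.5% |
| 0.5 | 4–11% | 23.5% | 23.0–26.6% |
| 1.0 | 15–26% | 7.2% | 8.1–10.7% |

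Type I error is 4.4–5.1% with all values kept, 4.7–5.1% with pooled limits and 5.4–6.4% with per-arm limits. Total cholesterol lies near the top row. Equation 1, with two-sided α of 0.05 and 90% power, implies an SD of 0.12 × √(n/(2 × 3.2415²)) of the mean. That is 14% if 60 is the total (n = 30 per arm) and 20% if 60 is per arm.

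**The case against.** The strongest objection is about scope. The outlier sentences do not say which variables they govern. The references to biomarkers and to every parameter belong to neighbouring sentences on the ANCOVA and the percent change. The list of dependent variables under Study Design omits ALT, AST, LDH, BUN and creatinine. This stands to the extent that coverage of the safety markers is an inference. It is a strong one: that list is not worded as complete, Hypotheses calls these markers biomarkers and predicts their between-group result, and no other analysis section or exemption is given.

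Second, the text is conditional, and the word for recalculation implies a first set of results with all values. Both are true, but nothing says that both sets are reported, and no counts are given.

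Third, a contrast with the diet records should not be pressed too far. The cut-off used there is also a statistical limit and needs no documented recording error. It does, however, test whether a record is plausible, and the number removed is given for each arm.

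Fourth, raw-scale ANCOVA with all values is not clearly better for strongly skewed efficacy markers. At log-SD 1.0 its root mean squared error is 0.398, against 0.276–0.304 after deletion. This stands, and it is why the fix asks for both results.

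A reader might also infer that the unstated choice of limits decides whether a cluster of three to five rises vanishes or stays. A bound for equal values suggests it: three values can reach at most √(27 × 29/(30 × 3)) = 2.95 SDs in an arm of 30, whereas five in a pooled 60 can reach 3.29. But at 34 per arm the bound for three is 3.17, and with realistic spread some but not all of the values are usually removed under either choice.

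**Conclusion.** The concern holds and should be fixed. As written, the rule can delete a genuine isolated rise in a safety marker from the mean, SD and percent change, with no stated place where the value would still be seen. At an assumed log-SD of 0.4, a 5-fold rise is nearly always removed, a 3-fold rise more often than not, and a 2-fold rise in about a quarter of cases. The probabilities depend on the assumed distribution; that the rule can remove a lone high value does not.

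Three stronger readings are not supported:
- **That safety values were in fact deleted.** The documents do not say so; without counts, a reader cannot tell.
- **That deletion hides a significant safety difference.** For a single rise, deletion does not lower the test's rejection rate. A loss of rejection appears only when several participants rise together.
- **That the rule seriously distorts efficacy.** Estimates shrink toward zero, slightly for a marker like total cholesterol and more only under strong skewness, with little change in power or type I error.

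**What to change.** - **Safety markers.** Do not apply the 3-SD rule to ALT, AST, LDH, BUN or creatinine. Keep all their values in the summaries and list the extreme values by arm.
- **Other markers.** Report results with and without the 3-SD exclusion side by side. State whether the limits are pooled or per arm, which time points they cover, whether the check is repeated, and the number removed per marker and arm.
- **Clearly right-skewed markers.** Add ANCOVA on log values. The section includes a Shapiro–Wilk test ("To check the assumption of normal distribution") but states no consequence if it fails.
- **Labelling.** Mark every analysis that departs from the Statistical Analysis section as chosen after data collection.

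The cost is revised wording and a re-run of existing models on data already held. Keeping all values gives larger standard errors: about 1–2% at log-SD 0.2, 9–11% at 0.5 and 40–43% at 1.0. Log ANCOVA recovers some of this. Rejection at the 12% effect is 27.0% against 23.5% for raw-scale ANCOVA with all values at log-SD 0.5, and 10.4% against 7.2% at 1.0. Its price is that the effect is reported as a ratio.
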